8. STATISTICAL CONSIDERATIONS AND ANALYTICAL PLAN

8.1. Sample size:

There is very little information regarding patient perspective for AEs.

Table 15 presents information regarding AEs in previous PFDN trials that have included pelvic organ prolapse repair, specifically apical suspension procedures.

Table 15. AEs in Prior PFDN Trials Including Surgical Treatment for Apical Prolapse

PFDN Trial	Total Number of Patients in Trial	Number of SAEs	Number of AEs Possibly Related to Study	Unexpected AEs	Total AEs
SUPeR	184	18 AEs	~60% of total AEs		300 AEs
OPUS	337	52*	219 AEs	31*	302 AEs

PFDN Trial	Total Number of Patients in Trial	Number of SAEs	Number of AEs Possibly Related to Study	Unexpected AEs	Total AEs
OPTIMAL	374	84 SAEs (but only 14 likely related to study)	160 patients		? 244 patients
ASPIRe	363				

^{*}Includes events likely unrelated to study (e.g. colon cancer, knee fracture, goiter)

An analysis of the SUPeR data available at the time of protocol development indicated that approximately 300 AEs had been reported, with slightly more than 60% having a relationship of possibly related or greater to the intervention. Approximately 50% of women had reached the 1-year follow-up for SUPeR at that time. Based on this information, we estimated that 400 AEs would be identified for ASPIRe that would be possibly related to the study, including all grades. Assuming that the distribution of severity is comparable to that found in the SUPeR trial, this study is powered to provide an interval estimated for the agreement between clinician grading of +/- 0.11. That is, if the study estimate of Kappa measuring the agreement is 0.5, we will be 95% confident that the true agreement is in the range of 0.39 to 0.61.

8.2. Statistical methods:

Aim 1: To compare patient vs. routine rankings of AE/symptom grade.

We will compare the proportions of AE rankings based on grade using Chi-square between patient and usual rankings. We will also determine the inter-rater agreement between the two groups by estimating the Cohen's Kappa coefficient. In addition to these tests, which provide an overall assessment of whether or not the ratings between clinicians and patients agree or disagree, we will also use extensions of generalized linear models that are appropriate for the ordinal nature of these outcomes and the paired structure of the patient/clinician ratings to evaluate how patients and clinicians disagree should the initial tests suggest differences. Specifically, we will explore classes of events for which the rankings of patients are consistently lower or higher than those of the clinicians.

Aim 2: To estimate the association between patient rankings of AE/symptom grade to Decision Regret and Decision Satisfaction in ASPIRe.

We will estimate the association between patient determined grade and impact of AEs and Decision Regret and Decision Satisfaction scores using linear model approaches. Mean scores for these scales will be compared between women who experienced serious AEs and different grades and impact of AEs. These scores will be compared at the 12 month and 3 year time points.

Aim 3: To estimate the association between AEs/symptoms and patient and quality of life and patient global impression outcomes (SF-12 and PGI-I).

We will utilize a combination graphical summaries and linear model-based approaches to compare the mean SF-12 and PGI-I scores between women who experienced severe AEs/symptoms and to compare these means across women who exhibit the different AE/symptom grades. These scores will be compared at the 12 month and 3 year time points.

Aim 4: To determine if patient perspective about AEs/symptoms changes over time.

We will determine the intra-observer agreement for patient rankings of AE/symptom grade and impact over time using weighted Kappa measures. We will also explore whether the impact of specific events plateaus over time, taking into account her perception of if and when the AE/symptom resolved.

Aim 5: To compare AE/symptom severity ranking between patient rankings and the Pelvic Floor Complication Scale.

We will develop a list of AEs, using the previously published Pelvic Floor Complication Scale (PFCS) as a guide. Appendix B-1 presents AEs ranked by severity based on physician rankings for the PFCS. We will develop a similar ranking list based on our patient rankings by AE grade and qualitatively compare and describe differences and similarities between these two ranking lists.

Aim 6: To begin to develop a shared model of AE/symptom reporting, incorporating both patient and clinician input.

Clinician reporting of adverse events is highly associated with clinical endpoints of death and hospitalization in cancer trials, as their impressions are based on professional training and experience. Patient reporting is more highly associated with measures of day to day health status and better reflects the short and or long-term impact of AEs. Therefore, these are complementary perspectives and a shared reporting model is likely ideal. We will work to develop a shared reporting model.

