7. DESCRIPTION OF STUDY INTERVENTIONS

The PPAR AE Log form will be similar to the Standard AE Log Form used for the usual ranking process to capture the PPAR attributes (grade/severity at its worst, impact, frequency). The 6-week and 6-60 month postoperative ASPIRe visit forms will include the PPAR inventory items under "Subject Reported Complications Table" to streamline capture from the coordinator standpoint. PPAR items on these forms will be highlighted using a mechanism such as an *asterisk to alert the coordinator that additional PPAR forms will be required for those AEs/symptoms.

We will collect PPAR data at the time points outlined in Table 14.

Table 14. Collection of Patient-Perspective Information for AEs

Time point	Rationale
Initial identification of AE	Provides patient's initial perspective *This gets updated at each interaction such that the "most severe" reporting by the patient gets recorded.
12 months postop	Provides information about whether her perspective changed over time
3 years postop (or final visit)	Provides her final perspective about the AE at the primary endpoint of the ASPIRe trial

When a PPAR AE/symptom is identified, the research staff will capture the PPAR AE/symptom attributes with the patient. The research staff will complete the usual process as needed to complete the Standard AE Log Form as well as the PPAR AE log Form. The investigators will be masked to the patient reporting and the patients will be masked to the investigator reporting. The attributes will be captured in an ongoing fashion such that the highest severity reported by the participant will be recorded on the PPAR AE log. Her perspective will be reassessed at 12 months and 3 years postoperative. Whether or not (and when) the AE/symptom has resolved will be determined based on the Standard ASPIRe AE log form by the field "Event End Date".

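### PPAR Aim 1 compares patient and clinician grades of the same adverse events with an ordinary chi-square, which ignores the pairing and loses substantial power for modest shifts

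*Protocol*

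**What the plan says.** Under Protocol Appendix B, section 7, when a PPAR event is identified the research staff "complete the Standard AE Log Form as well as the PPAR AE log Form". The same event therefore receives a clinician-side grade and a patient grade.

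Section 8.2, Aim 1 then sets out three steps:
- a comparison of grade distributions: "We will compare the proportions of AE rankings based on grade using Chi-square between patient and usual rankings";
- an agreement measure: "We will also determine the inter-rater agreement between the two groups by estimating the Cohen's Kappa coefficient";
- ordinal models that respect "the paired structure of the patient/clinician ratings", to be used to "evaluate how patients and clinicians disagree should the initial tests suggest differences".

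Pairing is mentioned only for the third step. No paired form of the chi-square is named, and nothing says how the first two steps combine to trigger the third.

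Section 8.1 sizes PPAR on the precision of kappa alone. It expects about 400 possibly related events and a 95% interval of 0.39 to 0.61 around a kappa of 0.5. It gives no alpha, target difference or power for the chi-square. SAP section 3.2 leaves PPAR to a separate SAP, which is not among the documents.

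**The concern.** A chi-square comparing grade proportions between two raters is naturally read as a rater-by-grade table. That table counts 400 doubly graded events as 800 independent grades. When the raters agree better than chance, their grades are positively correlated, and the independent-samples variance is too large for the difference being tested. The test then rejects too rarely, both under the null and when patients really do grade higher or lower.

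The other possible reading is a chi-square of independence on the patient-by-clinician cross-table. That tests association, so good agreement would give a significant result, the reverse of what Aim 1 asks.

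Appendix B hypothesises that the two gradings differ, and its results are meant to guide how the Network collects adverse events. A false finding of no difference would suggest that current grading already reflects patients' views. It could also weigh against running the only analysis in Aim 1 that models the paired grades directly.

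**Working it through.** **Inputs.** From Appendix B, 8.1: 400 events and kappa 0.5, with 0.39 and 0.61 as the limits of its interval. Assumed: two-sided alpha 0.05, which is the main SAP's default in 7.1, although PPAR lies outside that SAP. Also assumed: three grades split 50/38/12% or 80/15/5%. The protocol refers to the SUPeR severity distribution but does not print it.

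**The plan's own figure.** The half-width for kappa is 1.96 × √[po(1 − po)/n]/(1 − pe), with po = pe + κ(1 − pe).
- 80/15/5%: pe = 0.64 + 0.0225 + 0.0025 = 0.665 and po = 0.8325. The half-width is 1.96 × √(0.8325 × 0.1675/400)/0.335 = 0.109.
- 50/38/12%: pe = 0.25 + 0.1444 + 0.0144 = 0.4088 and po = 0.7044. The half-width is about 0.075.

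The stated ±0.11 is therefore attainable with a skewed split. It cannot be confirmed without the SUPeR distribution. It points towards the 80/15/5% end of the range.

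**Approximation for one grade boundary.** With equal margins, the paired variance of the difference is (1 − κ) times the unpaired variance. The unpaired test therefore uses an effective critical value of 1.960/√(1 − κ), which at κ = 0.5 is 2.772.
- True size: 2[1 − Φ(2.772)] = 0.006. At κ = 0.39 it is 0.012 and at κ = 0.61 it is 0.002.
- Where a paired test has 80% power, the unpaired test has Φ(1.960 + 0.842 − 2.772) = Φ(0.030) = 51%. At κ = 0.39 it has 62% and at κ = 0.61 it has 37%.
- Where a paired test has 90% power, the unpaired test has 68% at κ = 0.5.
- Pairs needed to regain 80% power: 400 × [(2.772 + 0.842)/(1.960 + 0.842)]² ≈ 665.
- With 20% of events in the higher category, the paired standard error is √(2 × 0.2 × 0.8 × 0.5/400) = 0.02. The difference detectable at 80% power rises from 2.802 × 0.02 = 5.6 points to 3.614 × 0.02 = 7.2 points.

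**Simulation with three grades.** The setting is 400 pairs from a bivariate normal, kappa about 0.5, with the patient scale shifted upwards. The ordinary chi-square is compared with Stuart-Maxwell.

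| Shift | Ordinary chi-square | Paired test |
|---|---|---|
| 0 (size) | 0.4–0.9% | about 5% |
| 0.15 SD, 80/15/5% | 14% | 66% |
| 0.15 SD, 50/38/12% | 24% | 83% |
| 0.20 SD, both splits | 38–62% | 90–98% |
| 0.30 SD, both splits | 92–99% | little further gain possible |

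In proportions, a 0.15 SD shift raises the share above the lowest grade from 50% to Φ(0.15) = 56% under the first split. Under the second it rises from 20% to 1 − Φ(0.842 − 0.15) = 24.5%.

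A second simulation imposed the shift in percentage points (80/15/5%, κ = 0.5). It gave 36% against 75% at 6 points, 72% against 95% at 8, and 92% against 99% at 10. With 50/35/15% grades, a 10-point shift gave 77% against 96%.

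**The condition for the paired models.** In every simulated dataset the 95% interval for kappa lay below 1. If imperfect agreement counts as suggesting differences, the models always run and the condition is empty. If the chi-square p-value is what counts, a test with size under 1% controls access. The protocol does not say which applies.

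**The case against.** Five points can be made for the plan.

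- **Kappa is part of the condition.** A reader might infer that the chi-square alone decides whether the paired models are run. The documents do not support that: the condition refers to the initial tests in the plural, and kappa, which uses the pairing, is one of them. What stands is that no threshold or combining rule is given. Kappa also measures agreement, not whether patients grade systematically higher or lower.
- **The loss depends on the size of the shift.** A reader might infer that the test lacks power across the board. It does not: at 0.30 SD it reaches 92 to 99%. Because the protocol names no target difference, the loss can be called neither severe in general nor harmless.
- **Clustering is not modelled.** About 400 events in 363 women means some women may contribute several, which changes the variance of both tests. The sizes and powers above are therefore indicative. Stuart-Maxwell also assumes independent pairs and a common set of categories. Tables 12 and 13 differ at the top: the clinician scale ends in life-threatening and death, while patients rate symptoms up to very severe. By the count in 5.2, 11 of 18 items are symptoms. A direct swap of tests is not quite enough.
- **PPAR has its own SAP.** It may name a paired test, and the protocol already recognises the pairing for the later models. But the method in 8.2 is the one on record, and an unseen document does not correct it.
- **The consequences are contained.** PPAR is supplementary. The error is conservative on the natural reading, and it does not touch the trial's primary or safety conclusions. That limits the weight of the point without removing it.

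**Conclusion.** Wrong as written. An ordinary chi-square is not a valid comparison of two gradings of the same events. Under the assumptions stated above, it is very conservative at the protocol's own planning values and gives up most of the available power for shifts near 0.15 SD. A material loss remains at 0.20 SD and little from about 0.30 SD. The direction follows from the pairing and any positive agreement. The exact figures rest on the assumed alpha and grade splits, and on treating events as independent.

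The condition for the paired ordinal models is a separate, lesser defect. It is undefined, and the documents do not show that the chi-square by itself would shut those models out.

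**What to change.** In Protocol Appendix B, 8.2, Aim 1, and in the PPAR SAP:

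1. Map the patient and clinician grade categories in Tables 12 and 13 to one common scale before any comparison.
2. Replace the chi-square with a paired marginal-homogeneity test (Stuart-Maxwell or Bhapkar), or make the already planned paired ordinal model the Aim 1 comparison. In either case allow for several events per woman.
3. Run the paired ordinal model regardless of the initial results, and delete the condition. Keep kappa as the measure of agreement.

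This needs no new data. The cost is a small amount of extra specification, chiefly the category mapping and the clustering, and some added analysis work.

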Aim 1: To compare patient vs. routine rankings* of AE/adverse symptom grade.

This aim will provide information about the relevance and severity of AEs/symptoms from the patient perspective via a ranking process and will also compare patient rankings with our current routine ranking process.

We hypothesize that the patient ranking and routine ranking processes will result in differences in perceived severity (grade).

Aim 2: To estimate the association between patient rankings of AE/symptom grade and impact to Decision Regret and Decision Satisfaction in ASPIRe.

We hypothesize that symptoms and events graded by patients as severe will be associated with higher Decision Regret and lower Decision Satisfaction scores compared to less severe events. This will provide data to inform which events are associated with harm (negative impact on decision-making and quality of life outcomes).

Aim 3: To estimate the association between AEs/symptoms and quality of life and patient global impression outcomes (SF-12 and PGI-I).

We hypothesize that symptoms and events graded by patients as more severe will be associated with decreased quality of life and global impression scores. This also provides data to inform which events are associated with harm.

Aim 4: To determine if patient perspective about AEs/symptoms changes over time.

We hypothesize that the patient perspective about adverse symptom and event attributes such as grade and impact on decision-making and quality of life outcomes will change over time and ultimately plateau. This will potentially provide information about the most relevant time points at which to measure specific events.

Aim 5: To compare AE/symptom severity ranking between patient rankings and the Pelvic Floor Complication Scale.

We hypothesize that AE ranking based on patient perspective compared to the PFCS will be different. Because the PFCS was developed by the PFDN, it is important to provide validity data from the patient perspective.

Aim 6: To begin to develop a shared model of AE/symptom reporting, incorporating both patient and clinician input.

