4. STUDY OBJECTIVES AND PURPOSE OF PPAR

Aim 1: To compare patient vs. routine rankings* of AE/symptom grade.

This aim will provide information about the relevance and severity of adverse symptoms and events from the patient perspective via a ranking process and will also compare patient rankings with the routine ranking process.

We hypothesize that the patient ranking versus routine ranking processes will result in differences in perceived severity (grade) and impact.

* "Routine ranking" is defined as the usual PFDN process for grading AEs, which typically incorporates research staff and investigator/surgeon input.

Aim 2: To estimate the association between patient rankings of AE/symptom grade and impact to Decision Regret and Decision Satisfaction in ASPIRe.

We hypothesize that symptoms and events graded by patients as severe will be associated with higher Decision Regret and lower Decision Satisfaction scores compared to less severe events. This assessment will provide data to inform which events are associated with harm (negative impact on decision-making and quality of life outcomes).

Aim 3: To estimate the association between AEs/symptoms and quality of life and patient global impression outcomes (SF-12 and PGI-I).

We hypothesize that symptoms and events graded by patients as more severe will be associated with decreased quality of life and global impression scores. This also provides data to inform which events are associated with harm.

Aim 4: To determine if patient perspective about AEs/symptoms changes over time.

We hypothesize that the patient perspective about adverse symptom and events qualities such as grade and impact on decision-making and quality of life outcomes will change over time and ultimately plateau. This will potentially provide information about the most relevant time points at which to measure specific events.

Aim 5: To compare AE/symptom severity ranking between patient rankings and the Pelvic Floor Complication Scale.

[figure not shown]
We hypothesize that AE/symptom ranking based on patient perspective compared to the PFCS will be different. Because the PFCS was developed by the PFDN, it is important to provide validity data from the patient perspective.

Aim 6: To begin to develop a shared model of AE/symptom reporting, incorporating both patient and clinician input.

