For PPAR, we will obtain patient input on pre-selected adverse events and symptoms through "active capture". The team recognized the main limitation of the active capture approach is that there may be AEs that patients consider important that may not be included in PPAR. However, we believe that for this supplementary study, active capture would be the most feasible approach to collecting data that is reliable. We believe this data will be meaningful and will allow us to begin the process of assessing the impact of AEs from the patient perspective.

We anticipate there will be adverse events that are discrete events (e.g. urinary tract infection) and others that are adverse symptoms (e.g. dyspareunia). For discrete adverse events, we will ask patients to grade the severity and rate the impact of the event. For adverse symptoms, patients will be asked to provide information about severity, frequency, and impact of the adverse symptom. This participant assessment will be referred to as "Patient Ranking" of AEs and is presented in Table 13.

Table 13. PPAR Adverse Event and Symptom Attributes

AE Descriptor:	Patient Question*	Response Options:
1. Adverse events		
Severity at its worse	How would you grade or rank this event?	Mild, moderate, severe, life-threatening
Impact	How much did the event/ symptom interfere with your usual or daily activities?	Not at all / A little bit / Somewhat / Quite a bit / Very much
2. Adverse symptoms		
Frequency	How often did you experience the symptom	Rarely, occasionally, frequently, almost constantly
Severity at worst	What was the severity level of the symptom at its worst?	Mild, moderate, severe, very severe
Impact	How much did the event/ symptom interfere with your usual or daily activities?	Not at all / A little bit / Somewhat / Quite a bit / Very much

5.2. Rationale for AEs/symptoms included in PPAR:

For the standard AE capture process in ASPIRe, AE capture will follow these guidelines:

- 0-6 weeks postop: All AEs grade 2 (moderate) or higher are captured.
- 6 weeks to 6 months: All AEs and SAEs involving death, hospitalization or ER visit, and grade 2 or higher at least possibly related to surgery in the opinion of the investigator are captured.
- After 6 months: Deaths, AEs and SAEs grade 2 or higher that are at least possibly related to pelvis or surgery in the opinion of the investigator are captured.

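### PPAR Aim 4 asks whether patients' adverse event ratings change and then plateau, but its only named statistic, weighted kappa, has no direction and can take the same value for symmetric noise as for a clear one-way shift

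*Protocol*

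**What the plan says.** Protocol Appendix B, section 8.2, states the question as "Aim 4: To determine if patient perspective about AEs/symptoms changes over time". The hypothesis, under PPAR Study Aims, is that "grade and impact on decision-making and quality of life outcomes will change over time and ultimately plateau". Table 14 in section 7 schedules ratings when the event is identified, at 12 months, and at 3 years or the final visit; the reason given for the 12-month rating is "Provides information about whether her perspective changed over time".

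The one statistic named for Aim 4 is in this sentence: "We will determine the intra-observer agreement for patient rankings of AE/symptom grade and impact over time using weighted Kappa measures". The type of weights is not stated. A second sentence adds "We will also explore whether the impact of specific events plateaus over time", taking account of resolution. It covers impact only and names no method.

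Aim 1, in the same section, also uses kappa but goes further. If patient and clinician ratings differ, it plans "extensions of generalized linear models that are appropriate for the ordinal nature of these outcomes and the paired structure of the patient/clinician ratings", and it will look for classes of events where one side is consistently lower or higher.

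Two further facts bear on the point. Section 7 and Table 14 update the initial severity at each contact so that the most severe report is kept. SAP section 3.2 places PPAR in a secondary manuscript with its own SAP, which is not among the documents reviewed.

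**The concern.** The question is about change over time, and the named statistic measures agreement beyond chance. These differ in three ways.

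- **Direction.** Exchanging the two ratings leaves weighted kappa unchanged, so a fall and an equal rise look alike.
- **Reference value.** Kappa's natural null is chance agreement (0), not absence of change. Its shortfall from 1 mixes retest noise with real movement.
- **Level.** A given kappa can come from noise around a stable rating or from reliable ratings that have all moved one way.

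Aim 4 is meant to help show when particular events are best measured. Kappa alone could leave a consistent softening or hardening of women's views unreported behind acceptable agreement, or could leave ordinary re-rating noise open to being read as change.

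**Working it through.** **The plan's own figure.** PPAR's only precision statement is a 95% half-width of 0.11 for kappa = 0.5 with 400 events. It concerns agreement with clinician grading (Aim 1). With half-width = 1.96 × sqrt(po(1 − po) / (n(1 − pe)²)), n = 400 and po = pe + 0.5(1 − pe), chance agreement pe = 0.25 gives 0.063, 0.50 gives 0.085 and 0.70 gives 0.117; 0.11 needs pe of about 0.67. The severity distribution is not given, so the figure is attainable but cannot be confirmed. Nothing comparable is given for Aim 4.

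**Constructed tables.** Inputs: four ordered grades ("Mild, moderate, severe, life-threatening", Table 13), 400 events (section 8.1) and, as an assumption, 100 events per grade at the first rating. Formula: kappa = 1 − (mean observed distance) / (mean distance expected by chance).

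- One-way shift: 50 events fall one step from each of grades 2, 3 and 4 (150 in all). Second-rating margins are 0.375, 0.25, 0.25, 0.125. Observed distance = 150/400 = 0.375. The average distance from a uniform first rating is 1.5, 1, 1, 1.5 for second-rating grades 1 to 4, so expected distance = 0.375 × 1.5 + 0.25 × 1 + 0.25 × 1 + 0.125 × 1.5 = 1.25. Kappa = 1 − 0.375/1.25 = 0.70.
- Symmetric re-rating: 75 rise and 75 fall one step, margins unchanged. Observed distance 0.375, expected 0.25 × (1.5 + 1 + 1 + 1.5) = 1.25. Kappa = 0.70.
- Quadratic weights: expected 2.5 in both tables, kappa = 1 − 0.375/2.5 = 0.85 in both.
- A directional summary separates them. Mean change is −150/400 = −0.375 grade against 0; the sign statistic is −150/√150 = −12.2 against 0.

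On the five-level impact scale with equal margins and 40% moved, kappa is 0.75 (linear) and 0.90 (quadratic) in both cases. With an assumed skewed baseline (45/35/17/3%) and equal numbers moved, the values are close but not equal: 0.685 (symmetric) and 0.667 (one-way) at 27.5% moved, 0.496 and 0.448 at 44%, linear weights.

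**Simulation.** Assumptions: latent normal severity cut to 35/40/20/5%, 400 independent events with two ratings each, 1,000 data sets, linear weights. The paired test is of mean shift at the two-sided 5% level.

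| Retest correlation | True shift (SD) | Mean kappa | Mean grade change | Paired test rejects |
|---|---|---|---|---|
| 0.85 | 0 | 0.62 | 0.00 | about 5% |
| 0.95 | 0.4 down | 0.64 | −0.29 | 100% |
| 0.95 | 0 | 0.78 | 0.00 | about 5% |
| 0.85 | 0.4 down | 0.54 | about −0.29 | 100% |

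The first two rows have overlapping 95% ranges for kappa (0.57 to 0.68 and 0.59 to 0.70). The last two show that at fixed reliability a shift does lower kappa, from 0.78 to 0.64 or from 0.62 to 0.54. Reliability is not known in advance, so the level of kappa does not reveal which situation holds.

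**Running maximum.** The no-shift case was repeated with the initial value taken as the larger of two ratings (the number of updates is an assumption). The paired test of initial against a single later rating then rejects no shift in 100% of data sets at correlation 0.85 (apparent fall 0.17 grade) and in 99.8% at 0.95 (0.10 grade). Kappa stays at 0.63 and 0.78, so it does not show the artefact either.

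**The case against.** Several points on the other side stand.

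- A reader might infer that kappa always gives the same value for noise and for a shift. It can, but need not: values differ modestly under skewed margins, and at fixed reliability a shift lowers kappa.
- A reader might infer that the team would declare change whenever kappa falls below 1. No such rule appears; kappa is to be estimated.
- The hypothesis states no direction. Within-woman stability is a fair reading of it, and intra-observer agreement speaks to that. A mean-shift contrast would miss women moving in opposite directions.
- The plateau is not ignored. Higher agreement between 12 months and 3 years than between the initial rating and 12 months would be descriptive evidence of settling, and an exploratory look at impact is planned.
- A reader might infer that the timing of measurement in future trials rests on this answer. The protocol says only that Aim 4 may provide such information, and it presents PPAR as a beginning.
- The separate PPAR SAP may already specify a suitable model. That cannot be checked here.
- A directional test is not safe by itself: applied to the stored initial value, it would report a fall that did not happen.

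These limit the claim and shape the remedy. They do not supply a directional analysis for grade or a method for impact, and the Appendix B text is what the PPAR SAP would start from.

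**Conclusion.** The point holds in limited form. Weighted kappa, the only statistic named for Aim 4, cannot by itself say whether ratings rose, fell or merely varied: it is 0.70 for two tables whose mean change is −0.375 and 0 grade, and 0.62 against 0.64 in simulation for no shift and an unmistakable one. Grade has no directional analysis, and impact has an exploratory one without a method.

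The constructed-table result is arithmetic for equal baseline margins. The simulated values rest on an assumed rating distribution and assumed retest correlations, neither of which is in the documents. The 400 is the protocol's expectation for possibly related events of all grades, not a count of PPAR events with repeat ratings. Clustering within women was not modelled; it would widen intervals but leave the contrast. This is a minor, easily corrected matter in a secondary aim.

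**What to change.** In Appendix B section 8.2 and the PPAR SAP:

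1. Make the main Aim 4 analysis a repeated-measures ordinal model, fitted separately to severity and to impact, with time, random effects for woman and event, and resolution status from the adverse event log. This extends the type of model already foreseen for Aim 1.
2. Report the 12-month to 3-year shift with a 95% CI, and judge the plateau from that interval rather than from a non-significant test.
3. Report the initial to 12-month shift only if the initial value is the first rating the woman gave. If only the running most-severe value is available, label that contrast as biased downward.
4. Keep weighted kappa, with its weights stated, as a descriptive measure of consistency; it also reflects women who move in opposite directions.

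The cost is a few sentences and a little more analysis. The 12-month and 3-year ratings and the resolution dates are already planned. The one data question is whether the first rating is kept when the log is updated.
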